**PI Dr [name].**

**Co-PI Dr [name], Dr [name] Dr [name]**

**Goal:**

Assess the clinical impact of Buffered 1% lidocaine with epinephrine as compared to the Non-buffered 1% lidocaine with epinephrine in dental and oral surgical procedures.

**Background:**

Based on the discovery of its topical and locally injected anesthetic effects at the end of the 19th century, cocaine was rapidly adopted as a means of blocking painful sensory impulses from the periphery during surgical procedures.(1) In the last decade local anesthetics have been administered more often, alone or in combination with IV or inhalation anesthetics for most surgical procedures. For clinical procedures in the head and neck the local anesthetic drugs have been combined with a vasoconstrictor, usually epinephrine, to prolong the anesthetic effect at the locally injected anatomic site. To achieve pulpal and periosteal anesthesia by nerve or field block for procedures in dentistry, lidocaine at a 2% concentration has been preferred by clinicians for its reliable outcomes. To prolong the shelf life of the vasopressor, the drug combination must be formulated with a low pH, approximately pH 3.5 for lidocaine with 1/100k epinephrine (Epi).

With a better understanding of the pharmacology, new options for improving local anesthetic effectiveness including buffering the commercially supplied drugs to a neutral pH just prior to injection, continue to emerge.(2) When injected, the low pH causes the “sting” felt by patients on injection. Buffering to a neutral pH eliminates this discomfort and makes the maximum concentration of the non-ionized form of the anesthetic drug immediately available to the targeted nerve membrane.(3-7) Until recently, buffering local anesthetics containing Epi followed with bicarbonate just prior to injection was impractical for the quantities used in intraoral procedures. However, today we do have options to efficiently accomplish this buffering technique.(Anutra Medical, RTP, NC).

Buffering local anesthetics just prior to use produces positive outcomes including less “sting” on injection, faster onset of the drug, and possibly added drug potency, ie the same positive clinical effect at lower dosage. In pilot studies with healthy adults as their own controls Phero et al and Warren et al have shown that Buffered 1% lidocaine with 1/100k Epi was as effective as Non-buffered 2% lidocaine with 1/100k Epi for pulpal anesthesia on a 1st molar or canine after nerve block in the mandible or field block in the maxilla-Phase one of this study.(8,9) These outcomes could be beneficial for performing multiple procedures in children whose lidocaine dosage is limited by body weight or others with chronic liver disease.

**Rationale:**

The recently reported results from the two clinical studies involving buffered lidocaine with Epi have led to clinicians questioning whether the Buffered 1% lidocaine with Epi might be as effective for achieving pulpal and periosteal anesthesia for dental procedures as Non-Buffered 1% lidocaine with Epi-Phase two of this study, outcomes not usually considered by most clinicians. This protocol addresses that question.

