**Hypotheses:**

No differences exist in anesthetic depth for pulpal anesthesia after intraoral injection for maxillary field block(Phase one) or mandibular nerve block between Buffered 1% lidocaine with 1/100k epinephrine as compared to Non-buffered 1% lidocaine with 1/100k epinephrine.

**Study Time Frame: 6 months**Month One

IRB approvals. Prepare case-books.

Months Two-Three

Recruit 24 volunteers as subjects.

Clinical Study

Months Four-Five

Analyze data

Month Six

Prepare Abstracts, Papers

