**Data Collection/Analysis:**

Data will be managed by [name] and staff. Data collection forms for clinical data will be developed to use Teleform for direct scanning input into an ACCESS database. Similar forms have been used in previous studies including three with local anesthesia. All databases are stored on a password protected School of Dentistry server with specific group assignment. SAS will be used for database management and statistical analysis. Descriptive statistics are used to verify correct entry through range and logical checks.

**Statistical analysis Each Phase** .....Effect sizes are currently unknown for the difference in type of injection in time to onset of anesthesia or pain level during injection. Primary interest is the difference between type of injection. In order to check the assumption of negligible carryover effects an unpaired t-test or a Wilcoxon Rank Sum test, depending on the distribution of the outcome, will be used to compare the within subject sums of the results from sequence AB to the within subject sums from sequence BA. Under the assumption that the carryover effects are equal ( $\lambda_A = \lambda_B = \lambda$ ), the differences for every patient will be calculated and multiplied by  $\frac{1}{2}$ . The two sequences will be compared using a two-sample t test or a Wilcoxon rank sum test depending on the distribution of the outcome.

$$H_0 : \mu_{AB} - \mu_{BA} = 0$$

The expression:

$$\mu_{AB} - \mu_{BA} = 2(\mu_A - \mu_B)$$

so testing  $H_0 : \mu_{AB} - \mu_{BA} = 0$ , is equivalent to testing:

$$H_0 : \mu_A - \mu_B = 0$$

Sample Size: With a sample size in each sequence group of 12 (a total sample size of 24) a 2x2 crossover design will have 90% power to detect a difference in means of -10.00.(10)

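### The Rationale says the protocol addresses whether buffered 1% lidocaine is as effective as non-buffered 1%, but the plan offers only a zero-difference test, with no margin and no confidence interval.

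*Combined protocol and SAP*

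**What the plan says.** The Rationale asks whether buffered 1% lidocaine with epinephrine "might be as effective for achieving pulpal and periosteal anesthesia for dental procedures as Non-Buffered 1% lidocaine with Epi" and adds: "This protocol addresses that question". The Hypotheses section then states: "No differences exist in anesthetic depth for pulpal anesthesia after intraoral injection", for buffered against non-buffered 1% lidocaine, with no margin attached.

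Under Data Collection/Analysis, within-subject differences are halved and "The two sequences will be compared using a two-sample t test or a Wilcoxon rank sum test". The section explains that testing for no difference between the sequences "is equivalent to testing" a zero difference between the two solutions. The only other test is the carryover check. The section describes no equivalence or non-inferiority test, no confidence interval, and no rule for wording a non-significant result.

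Two statements bear on purpose and size. Methods says the primary interest is to estimate an effect size from a pilot, so as to judge whether a larger study is worthwhile. The analysis section says "Effect sizes are currently unknown for the difference in type of injection" for onset time and injection pain, yet ends by stating that with 12 per sequence "a 2x2 crossover design will have 90% power to detect a difference in means of -10.00".

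**The concern.** Asking whether one solution is as effective as another is an equivalence or non-inferiority question. It is answered by showing that the difference is smaller than some stated amount. A test of zero difference can show that the solutions differ. If it does not reject, it shows only that the data did not exclude zero, and in 24 subjects that can happen with a large true difference in either direction.

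The plan therefore has no valid route to the answer that the Rationale promises. It also has no interval to serve the estimation aim in Methods. What is at stake is the wording of the conclusion: with no rule in place, nothing stops an uninformative result from being described as no difference.

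A second point is that a difference alone does not show whether either solution works. The Background says 2% lidocaine has been preferred for its reliability, and this study has no 2% arm and no stated adequate level of anesthesia. Two 1% solutions that succeeded equally often and two that failed equally often would give the same difference.

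**Working it through.** **1. The plan's own figure.** Inputs from Data Collection/Analysis: 12 per sequence, mean difference 10 (sign ignored), power 90%. The SD, alpha, outcome and unit are not stated, so the 90% can be neither reproduced nor refuted. Let SDd be the SD of the within-subject period difference.

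- SE = (SDd/2) × √(2/12), with 22 df.
- Solving for 90% power at an assumed two-sided 5% (noncentral t) gives SDd = 14.4, so SE = 7.22 × 0.408 = 2.95.
- The 95% half-width would be 2.074 × 2.95 = 6.1.

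This cannot be the power for a 10-point difference on a single Yes/No pulp reading. For such a reading the variance of the within-subject difference is discordance − difference². Discordance is at least 0.10 when the difference is 0.10, so the SD is at least √(0.10 − 0.01) = 0.30, or 30 points, against the 14.4 required. The power statement gives no assurance about pulpal anesthesia.

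**2. How often the planned tests would miss a real difference.** From the documents: 12 v 12, halved within-subject differences, t test or rank sum test, Yes/No pulp test. Assumed: two-sided 5%, one reading (one tooth, time and test), no period effect, and discordance rates, none of which the documents give. Each subject scores +1, −1 or 0 (the two solutions differ in one direction, in the other, or agree). The true difference is the first discordance rate minus the second. Simulation with 20,000 runs per scenario:

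| Discordance | True difference | Not rejected, t | Not rejected, rank sum |
|---|---|---|---|
| 25% v 5% | 20 points | 56% | 58% |
| 30% v 10% | 20 points | 68% | 68% |
| 20% v 10% | 10 points | 87% | 88% |
| 35% v 5% | 30 points | 30% | 30% |
| 40% v 10% | 30 points | 43% | 44% |
| 45% v 5% | 40 points | 13% | 13% |

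**3. What an interval would show.** With an observed difference near zero, the half-width is about 1.96 × √(discordance/24):

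- 20% discordance: 1.96 × √(0.20/24) = 0.179
- 30%: 1.96 × √(0.30/24) = 0.219
- 40%: 1.96 × √(0.40/24) = 0.253

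An observed difference of zero would thus be compatible with true differences of about 18 to 25 points either way.

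**4. What a margin could deliver with 24 subjects.** Take 20% discordance and a true difference of zero, and ask only the one-sided (non-inferiority) question at 2.5%. Power is Φ(margin/√(0.20/24) − 1.96), where √(0.20/24) = 0.0913. The number needed for 90% power is 0.20 × (1.960 + 1.282)²/margin². The margins are illustrative; the documents give none.

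| Margin | Power, 24 subjects | N for 90% power |
|---|---|---|
| 10 points | 19% | 211 |
| 15 points | 38% | 94 |
| 20 points | 59% | 53 |

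Requiring both ends of the interval to lie inside the margin would lower these powers.

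**The case against.** The best case for the plan is that it describes a difference study. Both Goal statements and the Specific Aims speak of comparing, the analysis section names the difference between injections as its primary interest, and the power statement concerns detecting a difference. For this comparison the 'as effective' wording occurs once, in a sentence reporting what clinicians ask. A hypothesis of no difference is an ordinary null. Methods calls the study a pilot for estimation, so with 24 subjects a formal margin would mostly return an inconclusive answer.

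Much of this stands. It lowers the severity, and it makes an estimate with its interval a better main result than a margin-based claim. It does not close the gap, because the Rationale says the protocol answers the question and the analysis section plans no interval, even for the estimation aim.

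Four stronger readings are tempting and are not supported:

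- A reader might infer that a non-significant result will be reported as equal effectiveness. The documents nowhere say so.
- A reader might infer that non-rejection is the likeliest outcome. No effect size is given, and at 30 or 40 points the tests usually reject. The Background also suggests that buffering may help, and both arms receive 40 mg.
- A reader might infer from the Background's account of the earlier pilots that this is how they reached their 'as effective' conclusion. The documents do not say how it was reached.
- A reader might cite the exact McNemar test, where five discordant subjects all in one direction give p = 0.0625. The plan does not use that test. On the same data its own tests reject for every split across sequences (t test p = 0.010 to 0.024, rank sum p = 0.016 to 0.031).

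**Conclusion.** The concern holds in a limited form. The question posed in the Rationale and the test in the analysis section do not match, and no margin or interval connects them. The mismatch and the absence of a margin and an interval can be read directly from the text. The miss rates of about 56% to 68% at 20 points and 87% to 88% at 10 points, and the half-widths of 18 to 25 points, are illustrations. They rest on assumed discordance, one Yes/No reading, two-sided 5% and no period effect. The finding is that the plan cannot support an equal-effectiveness conclusion and does not guard against one; it is not that the investigators intend to draw one. It should be corrected before the data are unblinded, because it changes what the trial can properly conclude.

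**What to change.** In Data Collection/Analysis, make the main result the buffered minus non-buffered difference in the proportion of teeth anesthetized, with a 95% confidence interval that respects the crossover pairing. Report beside it the absolute proportion anesthetized for each solution, tooth and time, so that equal failure is not read as equal success.

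In Rationale and Hypotheses, state that a non-significant test will not be described as 'as effective' or as no difference, and will be reported as inconclusive with its interval. Add that 'as effective' may be claimed only if the sponsor fixes a margin before unblinding, for one named reading, and the interval lies within it. Naming the reading matters because two teeth, three post-injection times and two pulp tests give 2 × 3 × 2 = 12 candidates.

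The cost is wording only: no subject, visit or treatment changes. The drawback is that with 24 subjects the claim will rarely be available. That fits the pilot purpose in Methods, and the interval is what a larger study would need for its sample size.

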**Goal:**

Assess outcomes after mandibular nerve block anesthesia using Buffered 1% lidocaine with 1/100k epinephrine as compared to Non-buffered 1% lidocaine with 1/100k epinephrine.

**Specific Aims:**

Compare clinical depths of pulpal anesthesia for maxillary(Phase one) and mandibular(Phase two) molar and canine teeth at 30min intervals Post-injection

Assess pain levels during injection

Assess time after injection to lower lip numb

**Hypotheses:**

No differences exist in anesthetic depth for pulpal anesthesia after intraoral injection for maxillary field block(Phase one) or mandibular nerve block between Buffered 1% lidocaine with 1/100k epinephrine as compared to Non-buffered 1% lidocaine with 1/100k epinephrine.

**Study Time Frame: 6 months**Month One

IRB approvals. Prepare case-books.

Months Two-Three

Recruit 24 volunteers as subjects.

Clinical Study

Months Four-Five

Analyze data

Month Six

Prepare Abstracts, Papers

**Methods: Blinded, Randomized Clinical Design**

Recruit subjects with IRB approved consent at UNC

Obtain NIH clinical trial registration

Target enrollment of 24 subjects each phase, 48 total subjects.

Subjects will serve as their own controls in a cross-over AB/BA study design which is uniform within sequences, uniform within periods, and balanced

Sample size justification: Primary interest is estimation of effect size from pilot study. 24 subjects should be sufficient to provide data to assess whether a larger study is warranted and provide estimates for sample size calculation for larger studies.

Vital signs recorded: 10 min before, just after drug administration, and before discharge

Randomized subjects to be injected orally for Maxillary field block(Posterior superior and Palatal sensory nerves Phase one) or mandibular nerve block (Inferior alveolar, Lingual, and

Buccal sensory nerves Phase two) alternatively with 4cc of buffered 1% lidocaine (40mg.) with 1/100k Epi and 4cc non-buffered of 1% lidocaine(40mg.) with 1/100k Epi.

SAS will be used to create randomization schedules:

The randomization will be performed first to type of drug given with a balanced randomization (half subjects buffered; half to non-buffered)

An OMS faculty will administer the drugs in the OMS clinic.

In week One, Each subject would receive either the buffered or the non-buffered anesthetic to block the Inferior alveolar, Lingual and Buccal nerves.

At least a week later, longer than the 1.5-2hr. elimination half-life of the drug lidocaine,

injections for the nerve block would involve the alternate local anesthetic combination.

**Study Subjects: 24**

Inclusion Criteria

Age 18-30 years

ASA I

Willingness to participate in two sessions

Exclusion Criteria

Allergy to lidocaine class of anesthetic drugs

Local anesthetic drug use in past week

Current symptoms in teeth or oral mucosa

**Data Collection: UNC OMS clinic: Timed assessment pre, and post-anesthetic clinical effects**

**Clinical outcomes recorded from subjects' subjective responses**

Reported pain on injection: 10pt Likert-type scale anchored No pain, Worst pain imaginable

Time to lower lip numbness after injection for nerve block

Ipsilateral Mandibular teeth to be tested: 1st molar and canine

Assessment: pre, and post-anesthetic administration for pulpal anesthesia

Pulp Test/Response to electrical stimulation: Yes or No

Testing interval: Pre-local anesthetic, and

Post-local anesthetic at 30min, 90min, 120min.

Pulp Test/ Response to Cold: Yes or No

Testing interval: Pre-local anesthetic, and

Post-local anesthetic at 30min, 90min, 120min.

**Data Collection/Analysis:**

Data will be managed by [name] and staff. Data collection forms for clinical data will be developed to use Teleform for direct scanning input into an ACCESS database. Similar forms have been used in previous studies including three with local anesthesia. All databases are stored on a password protected School of Dentistry server with specific group assignment. SAS will be used for database management and statistical analysis. Descriptive statistics are used to verify correct entry through range and logical checks.

**Statistical analysis Each Phase** .....Effect sizes are currently unknown for the difference in type of injection in time to onset of anesthesia or pain level during injection. Primary interest is the difference between type of injection. In order to check the assumption of negligible carryover effects an unpaired t-test or a Wilcoxon Rank Sum test, depending on the distribution of the outcome, will be used to compare the within subject sums of the results from sequence AB to the within subject sums from sequence BA. Under the assumption that the carryover effects are equal ( $\lambda_A = \lambda_B = \lambda$ ), the differences for every patient will be calculated and multiplied by  $\frac{1}{2}$ . The two sequences will be compared using a two-sample t test or a Wilcoxon rank sum test depending on the distribution of the outcome.

$$H_0 : \mu_{AB} - \mu_{BA} = 0$$

The expression:

$$\mu_{AB} - \mu_{BA} = 2(\mu_A - \mu_B)$$

so testing  $H_0 : \mu_{AB} - \mu_{BA} = 0$ , is equivalent to testing:

$$H_0 : \mu_A - \mu_B = 0$$

Sample Size: With a sample size in each sequence group of 12 (a total sample size of 24) a 2x2 crossover design will have 90% power to detect a difference in means of -10.00.(10)

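### Does leaving the within-patient difference undefined turn the crossover drug comparison into a test of period?

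*Combined protocol and SAP*

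**What the plan says.** The trial is a two-period crossover (Methods: Blinded, Randomized Clinical Design): "Subjects will serve as their own controls in a cross-over AB/BA study design", described as "uniform within sequences, uniform within periods, and balanced".

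The drug comparison is in Data Collection/Analysis, under the statistical analysis for each phase. It states the target: "Primary interest is the difference between type of injection". It then checks carryover by comparing within-subject sums between the sequences. Next, assuming equal carryover (λ_A = λ_B), it says that "the differences for every patient will be calculated and multiplied by" ½, and that "The two sequences will be compared using a two-sample t test or a Wilcoxon rank sum test", depending on the distribution.

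The null follows, μ_AB − μ_BA = 0, with the identity μ_AB − μ_BA = 2(μ_A − μ_B). The plan concludes that the test is equivalent to testing μ_A − μ_B = 0. It gives 12 patients per sequence and "90% power to detect a difference in means of -10.00".

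The text does not give the order of subtraction, does not say which drug is A and which is B, and does not define μ_AB and μ_BA.

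**The concern.** Two within-patient differences are natural in an AB/BA design: first period minus second, and one drug minus the other. The instruction names neither. The analysis section never uses the word period, and the only difference it puts into words is the one between types of injection. An analyst working from the prose alone could therefore compute buffered minus non-buffered for every patient and compare the sequences on it.

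That comparison tests the visit effect. It would find no difference however large the drug effect, or would report a first-to-second-visit shift as a drug effect. This is the plan's only stated comparison of the drugs, and Methods says "Primary interest is estimation of effect size from pilot study". The printed factor 2 adds to the doubt, because it does not match the halved quantity on either choice.

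**Working it through.** **Inputs.** From the plan: 12 per sequence, difference -10.00, power 90%. Not in the plan: significance level, sidedness and SD. I assume two-sided 5% and solve for the SD.

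**1. The plan's own figure.** For a two-sample t test on halved differences, the noncentrality is |Δ| / (s√(2/n)) with 22 df. With Δ = 10 and n = 12, 90% power needs s = 7.22: 7.22 × √(2/12) = 2.95, and 10 / 2.95 = 3.39. That is an SD of 14.44 for unhalved differences, or 14.44/√2 = 10.21 within patient. If the unhalved SD were 10, 20 or 30, power would be 99.7%, 64.9% or 34.6%. So 90% can be neither confirmed nor refuted. The present point does not depend on it.

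**2. What each difference tests.** Write τ = μ_A − μ_B and π = period 1 minus period 2, with carryover λ_A or λ_B entering in period 2. Unhalved:

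| Difference | Mean in AB | Mean in BA | AB minus BA |
|---|---|---|---|
| Period 1 − period 2 | τ + π − λ_A | −τ + π − λ_B | 2τ − (λ_A − λ_B) |
| A − B | τ + π − λ_A | τ − π + λ_B | 2π − (λ_A + λ_B) |

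**3. Which row the plan describes.**
- *Null equivalence.* The plan says that a zero sequence contrast is the same as τ = 0. That holds in the first row under equal carryover. In the second row τ does not appear.
- *Carryover.* The plan assumes λ_A = λ_B. In the first row this removes carryover exactly. In the second it leaves −2λ, so the assumption would serve no purpose.
- *Identity.* The printed 2(μ_A − μ_B) is the first-row contrast under equal carryover, before halving.

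All three point to period 1 minus period 2.

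**4. The factor 2.** After halving, the first-row contrast is τ, so the multiplier is 1, not 2. Halving every value halves both the mean contrast and its standard error, so t is unchanged. It also preserves ranks, so the Wilcoxon result is unchanged.

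**5. Size if the wrong difference were used.** Simulated rejection rates: 12 per sequence, within-patient SD 10.21, 40,000 trials per row. The visit shift here is visit 2 minus visit 1.

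| Drug effect | Visit shift | Halved period differences | Halved A − B differences |
|---|---|---|---|
| -10 | 0 | 90.1% | 5.1% |
| 0 | 0 | 5.1% | 5.0% |
| 0 | -10 | 5.0% | 90.2% |
| -10 | -10 | 90.1% | 89.8% |
| -10 | +5 | 90.2% | 36.8% |

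In the first row the mean contrasts are -10.03 and 0.00. With the Wilcoxon test in that scenario (5,000 trials) the rates are 87.2% and 4.5%.

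**The case for a change.** The strongest case for a change is that a wrong choice would go unnoticed, since either difference yields a plausible p-value, and that clearer text would cost two or three lines. The equations that identify the right difference also conflict with the halving in the sentence before them. And since estimation is a stated aim, someone could take the halved contrast, apply the printed identity and report -5 for a true -10. With an SD of 7.22 on the halved scale, planning the next trial on 5 instead of 10 would raise it from 12 to 45 per sequence.

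The algebra and these figures stand, and so does the omission. The risk is much weaker. To run the period test by mistake, an analyst would have to set aside the stated null, the identity and the carryover assumption, all of which adjoin the instruction. The sentence about type of injection names the target of inference. It does not define a per-patient variable, and as a target it supports a test of drug. The 90% against 5% contrast is built in: the SD was chosen to give 90%, and 5% is the assumed level. It shows the cost of a reading that the plan excludes, not a likelihood of error.

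The estimation risk is also remote. The plan uses the identity only to justify the null and never to derive an estimate. Leaving A and B unassigned affects only the sign of the result, not a two-sided test.

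**Conclusion.** The concern does not call for a change. The plan leaves the order of subtraction unwritten, but its null equivalence, its identity and its equal-carryover assumption fit only period 1 minus period 2. An analyst following the whole paragraph runs a valid test of drug, and the mean contrast of the halved differences estimates μ_A − μ_B directly.

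The mismatch between ½ and 2 is a clerical slip. It changes no test statistic, p-value or power, and could mislead by a factor of 2 only through a step that the plan does not prescribe.

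The conclusion rests on the algebra and on equal carryover, which the plan itself assumes. The rejection rates rest also on the assumed two-sided 5% level and the back-solved SD, but the conclusion does not depend on them.
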